1.0 Objectives / Specific Aims

Preterm birth and complications in term births increase infant morbidity and mortality. Premature rupture of membranes, intrauterine or systemic infection, diabetes, fetal-maternal hemorrhage and abruption lead to fetal distress and preterm delivery or hypoxia ischemia at term birth. These conditions result in increased risk for intraventricular hemorrhage, global hypoxia-ischemia (HIE), arterial stroke, and neuroinflammation with white matter injury in newborns of all gestational ages (GA).¹⁻⁵ CNS injuries then may manifest as early developmental delays and motor weakness in the first 12 months, that presage hemiplegic cerebral palsy (CP).

Early targeted therapy interventions for high-risk infants aim to improve neurological outcomes by taking advantage of critical windows for neuroplasticity.^{4,5} Intensive interventions, such as constraint-induced movement therapy (CIMT), are designed to ameliorate early motor predecessors of CP in at-risk infants.⁶⁻¹³ This intervention must be provided at a minimally effective dosage of 40 hours,¹³ and 60-120 hours for optimal outcomes, and are typically provided in a condensed time period, over 4 to 6 weeks with intensive task-practice for 3-6 hours a day.⁶⁻¹³ Delivering CIMT within the context a typical family day is a challenge.¹¹ Interventional strategies that reduce the time requirement while offering the same or better outcomes would benefit families and facilitate treatment delivery.

Few studies have used neuromodulation combined with intensive motor therapies, such as CIMT, to enhance neuroplasticity and improve functional outcomes in children. Transcranial direct current stimulation has been used safely in older children with CP during bimanual learning therapy.^{14,15} Our group is the first to use non-invasive transcutaneous auricular vagus nerve stimulation (taVNS) paired with a motor task of bottle-feeding in infants with feeding failure. taVNS paired with motor feeding activity was safe and over 50%^{16,17} infants determined to need a gastrostomy tube (G-tube) attained full oral feeds (mean time to full oral feeds 15 days with once daily, and 7.8 days with twice daily treatment). With our unique collaboration of experts in brain stimulation, pediatric translational clinical science and pediatric occupational therapy in this pilot project, we are one of the few groups able to rapidly translate this neuromodulatory modality in older infants with hemiplegia undergoing CIMT treatment.

We propose to expand the paradigm of pairing neuromodulation with motor training in at-risk infants by **exploring the safety, feasibility, and effectiveness of delivering taVNS concurrently with CIMT**. Our hypothesis is that combining taVNS with intensive CIMT may boost neuroplasticity, allowing for delivery of infant therapy at a minimally effective dosage (40h)¹³ while improving infant outcomes.

Aim 1: To determine the feasibility and safety of taVNS in at-risk infants 6-18mo undergoing CIMT therapy in open label pilot trial. We will assess the therapist's ability to deliver high-quality CIMT while delivering taVNS stimulation by videotaping the sessions and scoring randomly selected weekly treatment (20% sessions) with a CIMT fidelity measure we and others have used in CIMT studies.¹³ Scores must meet or exceed therapist goals to show that taVNS can be delivered by the therapist without detracting from the delivery of high quality CIMT.

We expect in 6-18month old infants with unilateral motor weakness that taVNS paired with intensive CIMT will be safe and well tolerated and can be delivered with good fidelity by CIMT therapists.

Aim 2: To generate pilot data measuring infant response to 40h CIMT + taVNS stimulation in: 1) upper extremity motor abilities, 2) gross motor skills, and 3) individual treatment goals.

We expect infant motor skills to improve with 40h CIMT+ taVNS, from before to the end of treatment, with maintenance of motor skill gains at 3months after completion of CIMT (n=5 complete the course of CIMT+taVNS).

This is the first application combining neuromodulation and the proven intervention of CIMT in infants.

We need to show feasibility and generate pilot data in a small number of patients prior to submission of an NIH proposal on pairing taVNS and CIMT for rehabilitation of infants with hemiplegia after perinatal brain injury (see [name] Letter of Support). This application expands our success with our previous NM4R pilot grant, which culminated in a taVNS infant system designated as an FDA Breakthrough Device. We will use this device in a completely unexplored area of neuromodulation, that of taVNS paired with intensive CIMT rehabilitation in young infants. Our goal with this combination neuromodulatory strategy is to decrease the severity of clinical deficits in infants, to improve day-to-day living, ameliorate life-long motor deficits, and help both the child and their families.

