Therapist	Highly trained therapists trained in the principles of pediatric CIMT ³⁸ will use immediate and varied reinforcement, primarily verbal praise, smiles, and supportive gestures, to sustain the infant's attention, engagement, and enjoyment, then "shape" a movement by using prompts and increasing the demands for greater precision, strength, fluency (coordination), and speed, using technique of "successive approximations". The therapist implements a "MR3 cycle," of Movement, Reinforcement, Repetition, and Refinement, used in the I-ACQUIRE Phase II clinical trial to progress the child in increments as skills increase
Components of infant CIMT	Sessions will actively engage the infant to initiate, attempt, repeat, practice, and refine a wide range of age developmentally appropriate skills and movements using the more-impaired arm and hand. Emphasis will be on engagement of the infant and the affected upper extremity in age- appropriate activities in positions of supine,

sessions	prone, sitting, quadruped, and supported standing.
Documentation for each session	Therapist will keep formal daily therapy logs and ask mothers to report on activities and progress at each session. Therapist and mothers will jointly review targeted therapy goals at each session.
Discharge program	Therapist and parents develop a practical written plan to maintain gains made during the CIMT program. The plan will involve motor skills and functional activities appropriate for the infant's age at discharge from the program.

Technical administration of taVNS: The therapist will need assistance with learning the taVNS trigger system and integrating it with CIMT. 1) We will provide training sessions for the single designated CIMT therapist who will perform all interventions before enrolling patients, and 2) the BSL RA will supervise and assist with taVNS treatments with each patient session. The brain stimulation RA will be trained to deliver stimulation, place the ear electrode for good impedance readings, and demonstrate this with [name] or [name] prior to supervising the CIMT therapist. We have several RAs who are experienced in infant taVNS who may also supervise any new RAs in the procedures. As part of this training, we have an instructional video for setting up the taVNS system with an infant.

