Limitations and alternative approaches: The therapist may provide feedback that a different trigger switch is needed or a different program with a '2min on-30sec-off' loop that does not require pressing the button repeatedly. We will then incorporate this feedback in our next design of the trigger. Previous NIH reviewers of our similar Soterix-based BabyStrong STTR phase I were concerned about overstimulation, requesting a fail-safe stop time for each trigger. We are using the same infant-modified Soterix taVNS unit, and for establishing safety in this CIMT+taVNS pilot we will use the same duty cycle of 2min-on, 30sec-off. For safety the taVNS unit limits deliverable microcurrent is limited to a maximum of 2mA, which is sufficient for adults to register a tingling. Feasibility of using wired ear electrodes: The infant should be engaged during CIMT such that the ear electrode does not irritate the infant. If the first infant does not tolerate the ear electrode, we will train infants on the electrode by having the mother place the electrode on the ear prior to the session and at home, to get the infant used to ignoring the presence of the electrode. The electrode should not impact hearing during the session. In our pilot trial infants received a hearing screen before discharge, all infants passed the screen except one, and that infant failed the hearing screen before taVNS treatment was initiated. No hearing adverse events were noted in that pilot trial.

Feasibility of delivering high fidelity CIMT with taVNS: We expect the therapist to maintain high fidelity of CIMT delivery while delivering taVNS over the weeks of treatment for the first infant. If the BSL RA has to assist in most therapy sessions after week 1, we will troubleshoot any sticking points and retrain the therapist so that the CIMT flow is minimally interrupted by triggering taVNS. If the therapist is not able to achieve high fidelity scores of 3 on all items by week 2 of treating the first infant, we will have the BSL RA assist with all sessions to ensure CIMT delivery, and if funds exist, incorporate design changes to increase therapist efficiency with the taVNS system during CIMT.

Aim 2: To measure infant response to low-dosage 40h CIMT + active taVNS stimulation (n=5) in: 1) upper extremity motor abilities, 2) gross motor skills, 3) individual treatment goals before and at the end of CIMT treatment. We will assess motor skills at 3mo after completion of CIMT for maintenance of gains.

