4.0 Study Endpoints

Aim 1: Primary CIMT feasibility outcomes: Ability of therapist to operate taVNS easily and successfully by earning a meeting or exceeding score (3 or 4) on random videotaped therapy sessions, as scored by CIMT fidelity treatment.

Aim 1: Primary taVNS safety and feasibility outcomes: Ability of infant to tolerate wired ear electrode and for electrode to remain securely in place with good contact with minor manipulation during sessions; <5% of sessions with sustained discomfort requiring decreasing current.

Aim 2: Primary Efficacy Outcome: We will use the Quality of Upper Extremity Skills Test (QUEST) subtests for grasp and dissociated movement as our primary outcome. The QUEST is a reliable, valid, quantitative outcome measure with excellent psychometric properties, and is recommended by NINDS/NICHD for the evaluation of movement patterns and hand function in children with cerebral palsy.⁴⁹ The subtests for grasp and dissociated movement have been used in published infant CIMT trials,⁸ and provide detailed information on hand function and quality of movement between the right and left sides of the body.

Aim 2: Secondary Efficacy Outcomes: We will use three other assessments for fine and gross motor function and meeting individual treatment goals: Developmental Assessment of Young Children (DAYC), the Gross Motor Function Measure-66 (GMFM-66) and the Goal Attainment Scale (GAS).

- The DAYC is a standardized assessment of early developmental skills from birth to 5 years of age⁵⁰ and is recommended for early detection of CP.⁵¹ We will use the DAYC Physical Development domain to assess developmentally appropriate fine and gross motor skills. [Mean (SD)=100±15 for each domain.]
- We will use the GMFM-66 as a comprehensive evaluation of foundational gross motor skills to assess how much of a task the infant can do rather than the quality of motor performance.^{48,52,53} Specific sections tested include Dimensions (A) Lying & rolling, (B) Sitting, (C) Crawling & kneeling, (D) Standing.^{52,53}
- The GAS is an individualized outcome measure that is standardized in order to calculate the extent to which a patient or group of patients' therapy goals are met.^{54,55} We will set individual goals for each infant and use the GAS scale to analyze differences between before and after CIMT+taVNS.

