10.0 Study Design / Methods

Overall Study Design: This study will determine the feasibility, and safety of therapist-directed taVNS paired with CIMT therapy in n=10, 6-18month old infants with hemiplegia after perinatally acquired brain injury. We will measure the effect of active taVNS paired with 40 hours of CIMT on infant motor skills before and after treatment over a month, and follow up the motor skills over 3 months. All infants will receive active taVNS treatment. CIMT treatment is a non-research procedure, and motor and developmental testing are non-research procedures. taVNS is a research procedure. CIMT sessions will be videotaped, to measure the fidelity of CIMT delivery while the therapist is delivering taVNS to determine feasibility.

The alternative treatment is the usual and customary occupational therapy services. If parents wish, they may pursue CIMT therapy with local therapists, but there are very few qualified therapists in the area.

We will monitor for and mitigate following risks are present with this study: Risk of skin irritation, risk of discomfort, risk of slightly decreased heart rate, and risk of loss of confidentiality.

Risk of skin irritation: we will monitor the skin on the inner aspect of the left ear before and after each session, and will switch to the right ear if redness is present, and decrease the stimulation if redness persists.

Risk of discomfort: We will protect against the risk of discomfort by close monitoring. We will use the mother's perception of infant discomfort and infant signs of discomfort to determine the perceptual threshold, and then treat at 0.1mA less than this level of perception. If any infant seems to be in discomfort during the CIMT taVNS session, we will decrease the microcurrent by 0.1mA, as in our feeding taVNS trial in infants. We will use facial expression change, fidgety movements and infant vocalization as signs of behavioral discomfort, to indicate need for decreasing the microcurrent during the taVNS session.

We will not continuously monitor heart rate during the taVNS session, as our extensive HR data in infants show no bradycardia and no decrease in HR beyond 60 seconds after starting stimulation.

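### Aim 1's fidelity mark can show that the CIMT standard was met while taVNS was delivered, but not that taVNS did not detract from CIMT, because no session is scored without taVNS.

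*Combined protocol and SAP*

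**What the plan says.** Section 1.0, Aim 1, sets the rule and the conclusion in one sentence. The rule is "Scores must meet or exceed therapist goals"; the purpose given for it is "to show that taVNS can be delivered by the therapist without detracting from the delivery of high quality CIMT". The section then states the expectation that the combined treatment "can be delivered with good fidelity by CIMT therapists".

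Section 4.0 makes this a primary feasibility outcome. The therapist succeeds "by earning a meeting or exceeding score (3 or 4) on random videotaped therapy sessions".

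The design sections fix what is scored:

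- Section 3.0 (Aim 1 and its procedures) has stimulation in each CIMT session. One randomly chosen session a week, 20% of sessions, is scored for fidelity with taVNS running.
- Section 10.0 states: "All infants will receive active taVNS treatment".
- Section 3.0 (technical administration) plans "training sessions for the single designated CIMT therapist who will perform all interventions". A research assistant supervises and helps with taVNS at each session.
- Section 3.0 (limitations) sets a trigger for more support: "If the therapist is not able to achieve high fidelity scores of 3 on all items by week 2 of treating the first infant". The research assistant then helps at all sessions.

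The Aim 1 paragraph of Section 3.0 words the conclusion less strongly than Section 1.0. There, scores at goal indicate that the therapist can give taVNS while also giving high-quality CIMT; nothing is said about detraction. The analysis paragraph in Section 12.0 does not mention fidelity.

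**The concern.** To say that one activity does not detract from another is to compare quality with it and quality without it. The plan collects only the first. It has no stimulation-free session, no score for this therapist before taVNS, no historical fidelity value and no allowable loss. A fixed mark answers a different question: whether quality was good enough.

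The distinction matters because this is a primary outcome, and Section 1.0 says the pilot is meant to show feasibility ahead of an NIH proposal. A no-detraction conclusion carried into that proposal would rest on data that cannot test it. The protocol itself treats interference as possible: Section 3.0 foresees retraining so that triggering interrupts CIMT as little as possible. The plural expectation about therapists also goes beyond scores that all come from one person.

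**Working it through.** **1. Reproduce the plan's figures.** Inputs are from Table 1 in Section 3.0: 2 hours per session, 5 sessions a week, 4 weeks.

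- Dosage: 2 × 5 × 4 = 40 hours, as stated.
- Sessions per infant: 5 × 4 = 20.
- Scored fraction: 1 of 5 per week = 20%, as stated.

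**2. Count the scored sessions.** Section 6.0 allows up to 10 infants and aims for at least 5 completed courses.

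- Per infant: 0.20 × 20 = 4.
- Five completed courses: 4 × 5 = 20. Ten: 4 × 10 = 40.
- Scored without taVNS: 0 in either case.

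The effect of taVNS on fidelity is the mean score with taVNS minus the mean score without it. The second term is never observed, so the difference cannot be estimated at any sample size.

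**3. Ask what the pass mark responds to.** The documents give no score distribution, so those below are assumptions. Two further assumptions: every scored session must reach 3, and sessions are independent. If q is the share of sessions below 3 under taVNS, then P(all pass) = (1 − q)^n. Mean losses count a score below 3 as 2 and treat the points as equally spaced, for illustration only.

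| Assumed scores without taVNS → with taVNS | Mean loss | q | n = 4 | n = 20 | n = 40 |
|---|---|---|---|---|---|
| All 4 → all 3 | 1.0 | 0 | 1.00 | 1.00 | 1.00 |
| 90% 4, 10% 3 → 10% 4, 90% 3 | 0.8 | 0 | 1.00 | 1.00 | 1.00 |
| 90% 4, 10% 3 → 30% 4, 60% 3, 10% below 3 | 0.7 | 0.10 | 0.66 | 0.12 | 0.01 |
| 90% 4, 10% 3 → 10% 4, 60% 3, 30% below 3 | 1.1 | 0.30 | 0.24 | 0.0008 | about 0 |

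For example, 0.9^20 = 0.12 and 0.7^4 = 0.24.

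The second row has a larger mean loss than the third (0.8 against 0.7). Yet the second always passes, and the third usually fails with 20 or more sessions. The rule reacts to scores crossing 3, not to the size of the change.

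**4. The reverse direction.** A score below 3 fails whatever its cause. With no taVNS-free score, a fail cannot be assigned to taVNS rather than to the infant, the session or the therapist's usual performance.

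**The case against.** The strongest reply is that the protocol says what it means by quality. Section 4.0 treats 3 as meeting the goal, and the limitations text in Section 3.0 calls 3 on all items high fidelity. On that reading a move from 4 to 3 is still high-quality CIMT, and the Section 1.0 phrase means only that the standard was kept. Section 3.0 states that conclusion without any comparison. The plan also watches for interference by other means: a weekly questionnaire to the therapist on ease of use, troubleshooting and retraining if the assistant is needed in most sessions after week 1, and the week 2 trigger. The plural is one sentence of expectation; the criterion and the endpoint speak of a single therapist. A fixed threshold is a reasonable feasibility criterion for an open-label pilot of 5 to 10 infants.

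Most of this stands. The threshold is sound for the question it answers, and the safeguards are real, though none supplies a score without taVNS. What does not go away is that two sections draw different conclusions from the same scores, and only the weaker one is supported. The assistant's presence at each session also means that a pass describes the therapist with support.

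**Conclusion.** The point holds as a limit on what may be concluded. Meeting the mark in all 20 to 40 scored sessions would show that the fidelity standard was met while one supported therapist delivered taVNS. It would not show an absence of detraction, nor extend to therapists in general. A loss within the passing range can still pass; a loss below 3 can be detected.

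The session counts follow from the documents. The pass probabilities rest on assumed score distributions, on every session having to pass, and on independence. The documents do not say how many sessions or items must reach 3 for Aim 1 overall, and sessions from one therapist are unlikely to be independent. A more lenient rule or positive correlation between sessions would make falls below 3 harder to detect than the table suggests.

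A reader might infer more, and the documents do not support it:

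- *That any real loss caused by taVNS would pass.* Not so: with 10% of sessions below 3, the chance that all 20 pass is 0.12 under the stated assumptions.
- *That this therapist will drop from 4 to 3, or that the drop is a given fraction of quality.* The therapist's usual score is not stated, and neither are the bottom of the scale or the spacing of its points.
- *That a hidden loss would weaken the Aim 2 motor response.* No figure in the documents links fidelity scores to motor outcome.
- *That the pilot needs taVNS-free sessions.* The narrower conclusion needs none. Videos of other infants taken before enrolment would differ in infant and time, need permission from non-study families, and still not isolate the effect of taVNS.

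**What to change.** Three edits, none of which touches treatment or data collection:

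1. In Section 1.0 (Aim 1), replace the no-detraction conclusion with one in line with Section 3.0, for example: *the CIMT fidelity standard was met while the single designated therapist, with research-assistant support, delivered taVNS*.
2. In the expectation sentence of Section 1.0, refer to this therapist instead of to therapists in the plural.
3. In Sections 4.0 and 12.0, state that the distribution of fidelity scores will be reported, with 3s, 4s and any lower scores shown separately by item, week and infant order, and not only as a pooled pass. This would make a drift from 4 to 3 over the study visible, although it still could not be attributed to taVNS.

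The cost is a slightly narrower claim and one descriptive table. Section 3.0 already refers to item scores, so no new scoring is needed.

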We have significant experience with taVNS for feeding failure in infants from our pilot trial of taVNS-paired feeding, who were refractory to standard of care early feeding interventions and were slated to receive a G-tube. We obtained IRB approval with medical device designation of non-significant risk for this open-label trial with parental consent.

Inclusion Criteria of previous taVNS feeding trial: Infants born ≤ 33 completed weeks gestation, or with brain injury (HIE); clinically stable; failing oral feeding; clinical team discussing need for G-tube with parents.

Exclusion Criteria of taVNS feeding trial: Cardiomyopathy, significant respiratory support

Primary Efficacy Outcomes: Increase in total daily oral feeding volumes compared before and during treatment, achievement of full oral feeds ($\geq 130\text{ml/kg/d}$ with weight gain), avoiding G-tube.

Secondary Efficacy outcomes: Brain changes measured by diffusion imaging (DKI) in white matter tract (WM) integrity before and after taVNS-paired feeding, normalized for weeks of development. Improvement in overall motor function by Specific Test of Early infant Motor Performance (STEP).⁴⁰

Primary Safety Outcomes: Bradycardia (HR<80bpm for 5 seconds), as potential effect of taVNS on the dorsal nucleus and efferent cardiac vagus nerve fibers; skin irritation; Change >3 points in the Neonatal and Infant Pain scale (NIPS).^{41,42}

Treatment Protocol:

- taVNS pulses delivered via a left ear electrode at 25Hz, pulse width 500 μ seconds.
- Perceptual threshold (PT) determined by increasing current slowly until infant detects tingling with facial change or shrug.
- taVNS delivered at 0.1mA $<$ PT, paired with suck-swallowing during one (n=15) or two (n=18) oral feedings per day, for 2-4 wks.

Fig. 1. Operator-controlled taVNS system: Baby bottle sleeve has a button trigger and wired connection to Soterix taVNS unit, with wired electrode on left tragus, as shown. We deliver taVNS by manual trigger coordinated with visible suck-swallow.

Results:

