5.0 Inclusion and Exclusion Criteria/ Study Population

- **Inclusion Criteria:** Infants, 6-18 months old with hemiplegia/motor asymmetry who qualify for CIMT, Gross Motor Function Classification System (GMFCS) level I-IV (a validated classification system with 5-levels that describe the gross motor function of children with cerebral palsy based on their self-initiated movements, in sitting, walking and mobility).⁴⁸ Prior CIMT therapy will be allowed if the infant has not had CIMT in the preceding 3 months.
- **Exclusion Criteria:** GMFCS level V,⁴⁸ severe motor impairment/quadriplegic involvement; uncorrected blindness or deafness, cardiomyopathy. CIMT therapy within the prior 3 months.

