12.0 Data Management

Analysis and Statistical plan: We will compare the change in score on functional measures between CIMT+ taVNS via repeated measures ANOVA from pre- to immediately and 30 days post- treatment via ANOVA. Power analysis on primary outcome is not valid with 5-10 participants. However, for reference in infants treated with 60 vs 120h intensive CIMT⁸, the QUEST grasp mean changed from 4.50 ± 2.6 to 5.25 ± 3.1 with 3h/day CIMT ($\Delta=0.75$), versus 4.14 ± 2.6 to 5.73 ± 3.0 with 6h/day CIMT ($\Delta=1.59$). We estimate 40h of CIMT+taVNS, 2h/day CIMT+taVNS will be similar to 3h CIMT, Δ grasp = 0.75 .⁸

Keeping Data Confidential: We will assign study numbers to each participant, keep CRF and consent forms in locked offices. Database files with names and contact information will be password protected and stored on the MUSC Pediatric server. All other data files related to this study will be identified by participant number only, without link to standard identifiers. We will publish the aggregate data only.

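### A held or higher QUEST or GMFM-66 score at 3 months cannot by itself show that a treatment gain was maintained, because the single-arm plan does not allow for development in infants aged 6-18 months

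*Combined protocol and SAP*

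**What the plan says.** The population in section 5.0 is "Infants, 6-18 months old with hemiplegia/motor asymmetry who qualify for CIMT". Treatment lasts 4 weeks (section 3.0, Table 1). Section 10.0 provides no comparator: "All infants will receive active taVNS treatment".

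Section 1.0 (Aim 2) expects improvement by the end of treatment, "with maintenance of motor skill gains at 3months after completion of CIMT". Section 3.0 repeats the purpose: "We will assess motor skills at 3mo after completion of CIMT for maintenance of gains". Neither section defines what would count as maintained.

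Section 4.0 makes the QUEST grasp and dissociated movement subtests the primary efficacy outcome. The GMFM-66, one of the secondary outcomes, covers lying and rolling, sitting, crawling and kneeling, and standing, and is used "to assess how much of a task the infant can do rather than the quality of motor performance". The plan gives no age norm or age adjustment for QUEST, the GMFM-66 or the Goal Attainment Scale. The remaining secondary outcome differs: "The DAYC is a standardized assessment of early developmental skills from birth to 5 years of age", and section 4.0 gives its mean of 100 and SD of 15.

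The analysis in section 12.0 begins: "We will compare the change in score on functional measures". It is a repeated measures ANOVA from before treatment to immediately after and 30 days after. It has no age term and does not name the 3-month visit.

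**The concern.** An infant who enters at 6 months is about 10 months old at the 3-month follow-up; one who enters at 18 months is about 22 months old. Rolling, sitting, crawling and standing are skills that infants acquire in this age range, and grasp plausibly matures too. With no untreated or CIMT-only group and no pre-treatment slope, the change in such a score mixes three things: the treatment effect, its later persistence or loss, and development. A score at 3 months that equals or exceeds the end-of-treatment score could mean that the gain was kept, or that it was lost and development made up the difference.

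The change from baseline to end of treatment has the same weakness over about 1 month instead of 4. The maintenance statement is more exposed because the interval is longer and because the absence of a decline is easily read as a positive finding. Section 1.0 says the pilot data are to precede a larger grant proposal, so an unqualified statement that gains were maintained could be carried forward as evidence of durability.

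**Working it through.** **Inputs from the documents.** Section 12.0 gives reference QUEST grasp means (SD) of 4.50 (2.6) to 5.25 (3.1) with 3 h/day of CIMT, and 4.14 to 5.73 with 6 h/day. It plans on the first of these changes. Treatment takes about 1 month, follow-up is 3 months later, and 5 to 10 infants are expected (sections 3.0 and 6.0).

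**Assumption.** Untreated growth in QUEST grasp is linear at *g* points per month. The documents give no value for *g*; the reference figures come from two treated groups, so they supply no untreated course either.

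**The plan's own figures.** 5.25 − 4.50 = 0.75 and 5.73 − 4.14 = 1.59. Both reproduce.

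**Break-even growth if the treatment gain is wholly lost by 3 months.** Follow-up minus baseline is then development alone, 4*g*.

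- Case A, where the 0.75 is an observed change that already includes 1 month of growth: the score looks fully held when 4*g* = 0.75, so *g* = 0.1875, about 0.19 per month (0.75/17 = 0.044 per week).
- Case B, where the 0.75 is pure treatment effect: the end-of-treatment change is 0.75 + *g*. The score looks fully held when 4*g* = 0.75 + *g*, so *g* = 0.75/3 = 0.25 per month (0.75/13 = 0.058 per week).

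Relative to the baseline SD, these are 0.1875/2.6 = 0.07 and 0.25/2.6 = 0.10 SD per month.

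**Apparent retention when true retention is zero.** Case A is 4*g*/0.75; case B is 4*g*/(0.75 + *g*).

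| *g* (points/month, assumed) | Case A | Case B |
|---|---|---|
| 0 | 0% | 0% |
| 0.05 | 27% | 25% |
| 0.10 | 53% | 47% |
| 0.15 | 80% | 67% |
| 0.1875 | 100% | 80% |
| 0.25 | 133% | 100% |

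**Would a test of decline help?** Take a paired t-test at two-sided 0.05, apply the SDs of 2.6 and 3.1 to the two visits, and assume a within-infant correlation *r* of 0.5 to 0.95. The SD of the difference is √(2.6² + 3.1² − 2·*r*·2.6·3.1), which runs from 2.88 down to 1.03. Power to detect a full 0.75-point decline is about 7-24% with 5 infants and 11-54% with 10. Even without any growth, a non-significant decline would not show maintenance.

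**Time points side by side.** Sections 1.0 and 3.0 place the maintenance assessment at 3 months after CIMT. The only analysis, in section 12.0, stops at 30 days after treatment. No stated analysis covers the visit on which the maintenance expectation rests.

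**The case against.** The strongest reply is that this is an open-label pilot meant to generate data, that the lack of a control is openly part of the design, and that section 12.0 itself concedes that a power analysis is not valid at this size. The plan states an expectation, not a pass/fail rule. A reader might infer that the maintenance expectation can hardly fail. The documents do not support that, because they set no criterion to pass or fail.

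The size is also open to challenge. The documents do not say that QUEST rises with age, and section 2.0 describes perinatal injury as disrupting the usual course of neural development, so growth in the affected hand may be slow. That stands: masking is possible, but not shown to be likely.

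A reader might also infer that the sponsor dropped a safeguard it had used before, since the feeding trial's imaging outcome was measured "before and after taVNS-paired feeding, normalized for weeks of development". That step belonged to diffusion imaging in a different trial and was never applied to motor scores. It shows only that the team knows the issue. This plan does include one age-standardised motor score.

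Finally, basing maintenance on the DAYC alone would be a poor trade. It is not specific to the affected hand, and a standard score can fall as peers advance while a trained skill is fully kept. That objection stands and limits the remedy.

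What the reply does not answer is the reading of the 3-month scores. A pilot needs no control arm, but it should not let a held raw score stand as evidence of a kept treatment effect.

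**Conclusion.** The point holds for interpretation. With one treated arm, entry at 6-18 months, about 4 months from baseline to follow-up and no age term, a held or higher QUEST or GMFM-66 score at 3 months does not by itself show that a treatment gain was kept. The case is clearest for the GMFM-66, whose items are developmental milestones, and plausible for QUEST grasp. The DAYC standard score is the exception, because average development alone would not raise it.

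The size is illustrative. Under linear growth, 0.19 to 0.25 QUEST grasp points per month would hide complete loss of a 0.75-point gain; slower growth would hide part of it, and zero growth none. A reader might infer that maturation will mask a loss in this trial. The documents give no rate, so they support only that it can. The point does not invalidate the pilot or its feasibility and safety aim; it limits what Aim 2 can conclude about durability, and the change is worth making.

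**What to change.** - In Aim 2 and section 12.0, state that a held or higher QUEST or GMFM-66 score at 3 months will not by itself be reported as maintenance of a treatment effect.
- Report QUEST and GMFM-66 changes descriptively, infant by infant, beside age at each visit and the interval between visits.
- Report the DAYC Physical Development standard score at every visit on one age basis, corrected with the gestational age already taken from the medical record (sections 10.0 and 13.0). Call it the age-referenced supporting measure, not the sole criterion, and give the two reasons: it is not specific to the affected hand, and it can fall relative to peers when a skill is kept.
- Keep QUEST as the primary efficacy outcome.
- Reconcile the 30-day time point in section 12.0 with the 3-month assessment in sections 1.0 and 3.0.

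The cost is protocol and analysis wording. No new visit or instrument is needed, provided the DAYC is among the motor assessments done at 3 months; section 3.0 does not list them by instrument, so the text should say so. The downside is a more cautious maintenance statement.
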